The 42-items questionnaire was developed originally in Danish in 1999 [51] and measures the structural aspect of social relations, with focus on contact frequency and diversity, and functional aspects with focus on perceived social support. CSRQ has been used in several Danish population-based surveys including in the Copenhagen Aging and Midlife Biobank (CAMB) [52]. In a sample of 38-69 old adults the CSRQ showed acceptable face and content validity and good test-retest reliability by 41% of the items had substantial to almost perfect agreement (kappa: 0.65-0.97) and the rest showed moderate agreement (kappa: 0.41-0.60) [53].

The secondary outcomes will also serve as follow up measurements six and 12 months after ending the intervention. They will also be conducted with online surveys.

13. Participant timeline

Time schedule of enrolment, interventions (including any run-ins and washouts), assessments, and visits for participants. A schematic diagram is highly recommended (see Figure).

[figure not shown]

Figure 1. SPIRIT participant timeline.

14. Sample size

Estimated number of participants needed to achieve study objectives is 128 participants. The number will be enough to show a 0.5 standard deviation difference between groups, equal to a moderate effect size. The number of participants will yield a power on 80% with a significance level on 0.05. To account for attrition this study will include 20% more participants than the above mentioned, and hence terminate the inclusion of participants when 154 participants in total and 77 in each group have been enrolled.

15. Recruitment

We will recruit participants through online advertisements on social media and in non-profit organizations working with older adults. We will also try to recruit participants at activity centers and other communities of older adults.

Methods: Assignment of interventions

16. Allocation

16.a. Sequence generation

Participants will be randomly assigned to either the intervention or the control group, with a 1:1 allocation. Eligible participants who have completed the baseline step count, will be randomized in blocks of four participants or more, stratified on sex (M/F) and average baseline step count for the extracted days prior to the allocation. Randomization of participants will happen every week, except weeks with less than four new participants.

16.b Allocation concealment mechanism

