The secondary outcomes are all participant reported and administered through SurveyXact. All participants will receive an email with an electronic SurveyXact invitation on the day of randomization. On the last day of intervention (day 84), the participants will receive a similar SurveyXact invitation with the end-point questionnaire. The six and 12-month follow up assessments will be administered in similar ways to the end-point assessment.

Demographic and other baseline items

Non-outcome variables will be included in the baseline questionnaire.

18b. Plans to promote participant retention and complete follow-up.

If possible, reasons for drop out will be collected from each discontinued participant. The available data on the primary outcome will be used to calculate the intervention period average steps per day. If the participant fails to synchronize the PAM and a possible drop out is suspected, a person from the research team will call the participant to either remind them to synchronize the PAM or try to motivate the participant to continue the intervention.

Lost to follow up with the end-point or follow up questionnaires will be reminded via email 7, 14 and 21 days after the deadline.

19. Data management

All outcomes will be handled and stored electronically.

Steps per day will be stored every time the participant synchronizes the PAM. The data handling responsible Fitrockr will extract data from the Garmin applications and store it according to the agreements. Every time a participant completes the intervention period, their data will be exported from the Fitrockr database and stored securely at the University of Copenhagen server.

During the study, with participants' verbal consent, telephone MI (and control) sessions is audiotaped on a regular basis to ensure fidelity of intervention delivery and to provide counselor feedback.

The participant reported outcomes for the secondary outcomes will be administered using SurveyXact, securing data every time a survey has been completed. Every time a participant completes the intervention period, their data will be exported from the Fitrockr database and stored securely at the University of Copenhagen server.

No personal data will be exported from Fitrockr or SurveyXact without pseudonymization. Complete anonymization of all data will be done after the last follow up period. Data protection agency approval Reference number: 514-0268/18-3000

20. Statistical methods

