The primary outcome will be analyzed as a mixed effects model, where intervention group are analyzed fixed and participants are random effects. The analysis will investigate the group difference in average daily step count, adjusted for baseline step count and gender. Same analysis will be performed on secondary outcomes.

Drop outs with data on the primary outcome for at least one week will have their average daily step count based on the available days. All analysis will be performed following the Intention to Treat (ITT) principle imputing missing data using a multiple imputation based on age, gender, baseline step counts and average daily step count (for missing data on the secondary outcomes). In

calculating the average daily step count, days with less than 100 steps will be handled as “days of non-wear” and excluded assessing the mean step count.

Methods: Monitoring

21. Data monitoring

Not applicable/relevant

22. Harms

In our study an adverse event will be defined as any untoward medical occurrence in a participant without regard to the possibility of a causal relationship with the intervention. Adverse events will be collected after the subject has provided consent and enrolled in the study. If a participant experiences an adverse event after the electronically administered informed consent has been signed (entry) but the subject has not started to receive study intervention, the event will be reported as not related to the intervention. All adverse events occurring after entry into the study will be recorded. The participants will be asked at the end-point questionnaire if they experienced any adverse events in terms of using the PAMs or trying to enhance their daily amount of physical activity.

23. Auditing

No auditing has been protocolled.

Ethics and dissemination

24. Research ethics approval

According to a written correspondence with the Danish Ethics Committee in the Capital Region of Denmark, this trial was not subject to the current laws on research ethics in Denmark due to the non-invasive behavioral change intervention. The study can be conducted without further approval from the Danish Ethics Committee in the Capital Region of Denmark (Journal-nr.:18004960).

25. Protocol amendments

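### The multiple-imputation model omits randomised group, so imputed values dilute the group difference the trial is meant to estimate

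*Combined protocol and SAP*

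**What the plan says.** Section 20 applies imputation to every analysis under the intention-to-treat principle, using "multiple imputation based on age, gender, baseline step counts and average daily step count (for missing data on the secondary outcomes". It does not name randomised group, and no other section adds it or says that imputation is done within arm.

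The analysis model in the same section is a mixed model in which "intervention group are analyzed fixed and participants are random effects". Its target is stated as follows: "The analysis will investigate the group difference in average daily step count, adjusted for baseline step count and gender". For the questionnaires the plan says "Same analysis will be performed on secondary outcomes".

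On who is imputed for the primary outcome, Section 20 says: "Drop outs with data on the primary outcome for at least one week will have their average daily step count based on the available days". Section 18b likewise uses whatever step data exist. In effect, steps are imputed only for participants with less than one week of data. The seven questionnaires have no such rule. They are collected by online survey at baseline, 12 weeks, 6 months and 12 months (Section 12). Section 18b plans for non-response: "Lost to follow up with the end-point or follow up questionnaires will be reminded via email 7, 14 and 21 days after the deadline".

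**The concern.** An imputation model should contain every term of the analysis model, above all the term whose coefficient is the trial's result. If group is left out, a missing value in either arm is drawn from the same pooled distribution, given age, gender and baseline steps. Imputed participants then show no arm difference of their own, and mixing them with observed participants pulls the estimate towards zero. For the questionnaires, average steps carry some of the effect into the imputed values, but only the part that runs through steps. Rubin's standard errors also stop matching the real sampling variability.

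At stake is a real effect being understated or missed because of the imputation rule. A complete-case analysis would not have this bias when data are missing completely at random.

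The predictor list also leaves out each questionnaire's own baseline score and its scores at other time points. These are collected and would ordinarily be the strongest predictors of a missing score.

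**Working it through.** **Plan's own figures (Section 14).** The plan says "The number will be enough to show a 0.5 standard deviation difference between groups, equal to a moderate effect size" and "The number of participants will yield a power on 80% with a significance level on 0.05". Two-sided, n per arm = 2 × (1.960 + 0.842)² / 0.5² = 62.8, so 63. The exact noncentral t gives 64 per arm, 128 in total, with power 80.1%. Then 128 × 1.20 = 153.6, so 154, or 77 per arm. The plan's 128 and 154 are reproduced.

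**Closed form, primary-type outcome.** Let δ be the true difference and f the imputed share in each arm. Observed participants differ by δ and pooled draws differ by 0, so the expected estimate is (1 − f) × δ + f × 0 = (1 − f)δ.

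**Simulation.** Inputs: 77 per arm; δ = 0.50 SD (Section 14); analysis of covariance on arm, sex and baseline steps, since each participant contributes one average; imputation from the listed predictors with and without arm; 20 imputations; Rubin's rules; 1,500 runs per scenario. Assumed: data missing completely at random and a baseline correlation of 0.5.

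| Imputed | (1 − f) × 0.50 | Mean estimate, no arm | Mean estimate, with arm | Power, no arm | Power, with arm |
|---|---|---|---|---|---|
| 5% | 0.475 | 0.476 | 0.502 | 91% | 93% |
| 10% | 0.450 | 0.450 | 0.501 | 87% | 91% |
| 20% | 0.400 | 0.402 | 0.504 | 75% | 89% |
| 30% | 0.350 | 0.346 | 0.500 | 56% | 82% |

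Further results:

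- Complete-case analysis at 20% missing gives 0.504 SD and 89% power, so imputing without arm is worse than not imputing.
- With a baseline correlation of 0 and 20% imputed: 0.402 against 0.506 SD, power 63% against 78%.
- With 16.9% imputed, the loss that takes 154 down to 128 (26/154): 0.5 × (1 − 0.169) = 0.416. The simulated value is 0.41 to 0.42, with power 66% against 79% at a baseline correlation of 0.
- With 30% imputed and a baseline correlation of 0.7, coverage of the 95% interval falls to 86–87%.
- With no true effect and 20% imputed, the rejection rate is 1.9% without arm and 5.2% with arm. The standard errors are too large and the test is conservative.

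**Questionnaire-type outcome.** Average steps enter the imputation model. Assume a 0.5 SD effect on both steps and the questionnaire, a baseline-to-steps correlation of 0.5, and a within-arm correlation r between questionnaire and steps. Given baseline, the pooled slope of questionnaire on steps is

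β = (0.75r + 0.5 × 0.5/4) / (0.75 + 0.5²/4) = (0.75r + 0.0625) / 0.8125.

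Imputed participants differ by 0.5β, so at 20% missing the expected estimate is 0.8 × 0.5 + 0.2 × 0.5β.

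| r | β | Expected | Simulated, no arm | Simulated, with arm | Power, no arm / with arm |
|---|---|---|---|---|---|
| 0.1 | 0.169 | 0.417 | 0.411 | 0.494 | 63% / 75% |
| 0.3 | 0.354 | 0.435 | 0.424 | 0.488 | 69% / 76% |
| 0.5 | 0.538 | 0.454 | 0.451 | 0.498 | 78% / 82% |
| 0.7 | 0.723 | 0.472 | 0.471 | 0.500 | 84% / 85% |

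At r = 0.3, imputed participants carry 0.5 × 0.354 = 0.18 of the 0.50 SD. At 30% missing the expected estimate is 0.7 × 0.5 + 0.3 × 0.177 = 0.40. Simulation gives 0.40 against 0.50 SD, with power 57% against 72%. Section 12 cites correlations with objectively measured activity of 0.30 for IPAQ-SF and 0.33 for NPAQ-short, so r near 0.3 is a reasonable reference for those two.

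**The case against.** **Few step outcomes will be imputed.** This stands as a limit on size. Anyone with a week of data keeps an observed mean, the monitor stores 30 days, and people who do not synchronise are telephoned. The plan gives no figure for the remainder, and the 16.9% above is the attrition allowance, not the imputed share. At 5% to 10% the loss is 0.02 to 0.05 SD.

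**The direction of bias is not certain for very early drop-outs.** Someone who leaves in the first week has had at most the first of seven calls. If such people gain nothing, the true intention-to-treat difference at 16.9% is itself about 0.5 × (1 − 0.169) = 0.416. Imputing without arm then lands close to it (0.414), while adding arm gives 0.502, which is too high. This is a fair point about an assumption, but the plan does not offer it as a rationale. It also does not cover people who received the intervention and later failed to return a questionnaire.

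**The error is conservative.** It does not raise the false-positive rate. In a superiority trial planned at 80% power, however, a diluted estimate and lost power are still defects.

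**The list may not be exhaustive.** The sentence does not say that only these variables will be used. Still, it names the predictors and leaves group out, and an analyst following it would omit group.

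**The analyst is blinded.** Section 17b anonymises the group names. The coded group already enters the analysis model and can enter the imputation model too.

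The omission of questionnaire baselines and other time points was not simulated. It is a secondary point, mainly about precision.

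**Conclusion.** The concern holds: the imputation rule is wrong as written. It omits the variable whose coefficient is the result, and following it shrinks the group difference by about the imputed share for steps and by somewhat less for questionnaires related to steps. For the primary outcome the loss is probably small, 0.02 to 0.05 SD at 5% to 10% imputed. For questionnaires at 20% to 30% missing and r = 0.3, the estimate falls from about 0.49–0.50 to 0.40–0.42 SD, and power falls by 7 to 15 percentage points. Measures only weakly related to steps come close to the full shrinkage.

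These sizes assume data missing completely at random, the same treatment effect in participants with missing data, and a 0.5 SD effect on the questionnaires borrowed from the sample-size section. The missing fractions and correlations are assumed ranges, because the documents give none for this trial.

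**What to change.** Replace the imputation sentence in Section 20, before the analysis, with wording to this effect: missing values will be multiply imputed from a model containing randomised group (as the anonymised code), age, gender and baseline step count; for each questionnaire the model will also contain average daily step count, that questionnaire's own baseline score and its scores at the other time points. Imputing separately by arm is an equivalent way to bring group in.

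If the investigators believe that very early drop-outs gain no benefit, that belief should be stated and examined in a named sensitivity analysis, not left implicit in the choice of predictors.

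The cost is one amended sentence and a few more variables in the imputation command. No new data and no unblinding are needed.

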The objective of this randomized controlled trial is to investigate if motivational interviewing provided as an add-on intervention to a physical activity intervention will increase the average daily step count in community-dwelling participants above the age of 70.

1. It is hypothesized that motivational interviewing, will enhance the average daily step count among participants.
2. It is hypothesized that motivational interviewing, will affect self-reported physical activity and quality of life.
3. It is hypothesized that self-efficacy and outcome expectancy for exercise, will mediate the effect and explain heterogeneity in the results.

8. Trial design

Study Type: Interventional

Estimated Enrollment: 154 participants

Allocation: Randomized

Intervention Model: Parallel Assignment

12-week intervention with two groups in a parallel design

Masking: Double (Investigator, Outcomes Assessor)

Primary investigator will be blinded for allocation before making the final analyses. No outcome assessments will be made by an assessor. Only objectively measured steps per day and participant reported outcome measures will be used for this study.

Primary Purpose: Prevention

The primary hypothesis will be investigated with a superiority analysis.

Methods: Participants, interventions, and outcomes

9. Study setting

Description of study settings (e.g., community clinic, academic hospital) and list of countries where data will be collected. Reference to where list of study sites can be obtained'.

This RCT will be conducted in Denmark. Participants eligible for inclusion will receive the content necessary for participation by mail. The participants will only have contact with the research team via phone or e-mail correspondence.

10. Eligibility criteria

Participants will be considered eligible for inclusion if they; 1) are retired and community-dwelling, 2) at least 70 years of age by the day of enrolling the trial, 3) own a smartphone or tablet able to install the *Garmin Connect application*, 4) have an email address and are able to correspond and complete the study survey on a computer and 5) have hearing abilities sufficient to receive a telephone interview.

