Participants will not be considered eligible for inclusion, and hence excluded, if; 1) they have cognitive impairment from moderate to severe dementia or Alzheimer's disease, 2) they are undergoing active chemotherapy or palliative care from cancer, 3) have a major mobility impairment (e.g. from paralysis, amputations, severe arthrosis or arthritis, Sclerosis or Parkinson's disease).

11. Interventions

Experimental: Motivational interviewing Experimental content + base intervention
	
Behavioral: Motivational interviews
 
During the 12-week intervention, the participants will receive seven telephone calls from a physical therapist (PT). Using an intervention schedule inspired by the work of King et al. to facilitate initiation and maintenance of behavior change, calls are delivered in week 1, 2, 3,5,7,9, and 12 [29].
 
The telephone call will consist of a motivational interview (MI) focused on enhancing the daily level of physical activity in the participants.
 
MI is a form of counselling aiming at prompting increases in self-efficacy, which may leave people more open to and invested in changing their behaviors and shows potential for significant effects for exercise behavior change. In this person-centered intervention model, participants are guided through self-reflective counseling. They receive feedback on these health behaviors in relation to national recommendations; consistent with a MI approach [27], this feedback also highlights the discrepancy between their health goals and their current health behaviors; they set collaborative goals for physical activity change with their PT, with the participant encouraged to begin with the target area in which she/he is most motivated to change; all of this is incorporated into a behaviorally-specific plan that specifies exactly what is to be done and when; barriers and supports are identified; confidence is assessed and problem-solving is discussed as necessary. These steps are repeated during intervention contacts, with goals being adjusted as necessary.
 
During the maintenance face (week 5-12) increasing emphasis is placed on identification of multi-level supports for health behavior change. Participants are encouraged to use a variety of supports including family and friends, as well as neighborhood and community supports. In collaboration with local community partners, a community reference

---	--

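### Section 22 sets no common route by which adverse events reach the record, and the interview arm has seven scheduled calls that control lacks, so recorded harms could be higher there at equal true rates

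*Combined protocol and SAP*

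**What the plan says.** Section 22 uses a broad definition: "an adverse event will be defined as any untoward medical occurrence in a participant without regard to the possibility of a causal relationship". It then states: "All adverse events occurring after entry into the study will be recorded". It does not say who records events or through which contact they are learned.

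The one method of asking that it names is a questionnaire item: "The participants will be asked at the end-point questionnaire if they experienced any adverse events in terms of using the PAMs", or in connection with trying to be more active. Section 18a gives the timing, with no distinction by arm: "On the last day of intervention (day 84), the participants will receive a similar SurveyXact invitation with the end-point questionnaire".

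Section 9 describes all contact as remote: "The participants will only have contact with the research team via phone or e-mail correspondence". Section 11 gives the interview arm seven physical therapist calls, in weeks 1, 2, 3, 5, 7, 9 and 12. Among other things, "barriers and supports are identified; confidence is assessed and problem-solving is discussed as necessary". For control, Section 11 describes a monitor and a pamphlet, and no calls.

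Two other places bear on contact with controls. Sections 11.b and 19 say that telephone sessions are audiotaped and mention control sessions in parentheses, without describing them anywhere. Section 18b provides for a call to a participant who stops synchronizing the monitor, and for collecting reasons for drop-out. Neither is limited to one arm.

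Sections 20 and 22 plan no between-arm analysis of adverse events.

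**The concern.** A promise to record every event can be kept only through whatever contacts occur. The day-84 item cannot keep it alone, because it asks about a narrower class of events than Section 22 defines, and it asks once. The remaining scheduled contact described for the 12 weeks is in one arm. A fall or a sore joint in week 5 could come up when a therapist discusses barriers to activity. A control participant with the same event has no described scheduled occasion to mention it before day 84.

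If events heard in calls go into the record, the two arms are observed with different intensity, and better wording of the questionnaire item would not change that. Section 31 says all results are to be published, and in a two-arm trial the reader will naturally set adverse events side by side by arm. An excess in the interview arm could not then be told apart from more contact, and similar counts could hide a true excess in control. The primary outcome, step count, is not affected.

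**Working it through.** **No stated figure to reproduce.** The documents give no adverse event rate, no capture probability and no harms comparison. The check therefore compares the routes into the record and then illustrates the possible size under stated assumptions.

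**Routes by which an event could reach the record**

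| Route | Interview arm | Control arm | Source |
|---|---|---|---|
| Day-84 item, monitor- or activity-related events | yes | yes | Sections 18a, 22 |
| Seven scheduled therapist calls | yes | none described | Section 11 |
| Control telephone sessions | – | mentioned, undefined | Sections 11.b, 19 |
| Call after lapsed synchronization | possible | possible | Section 18b |
| Reasons for drop-out | possible | possible | Section 18b |

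No section tells the therapist to ask about, log or forward adverse events. The link from calls to the record comes only from the promise to record all events.

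**Inputs.** Arm size is 77 (Section 14). The rest are assumptions:
- p: true 12-week risk, equal in both arms.
- q: share of affected participants captured by the questionnaire, equal in both arms.
- c: share of those missed by the questionnaire who are picked up in calls, interview arm only.

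**Formulas**
- Control recorded risk = p·q
- Interview-arm recorded risk = p·[q + (1 − q)·c]
- Ratio = 1 + c(1 − q)/q, which does not depend on p

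**Ratio at equal true risk**

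| q | c = 0 | c = 0.1 | c = 0.3 | c = 0.5 |
|---|---|---|---|---|
| 0.9 | 1.00 | 1.01 | 1.03 | 1.06 |
| 0.6 | 1.00 | 1.07 | 1.20 | 1.33 |
| 0.3 | 1.00 | 1.23 | 1.70 | 2.17 |

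For example, at q = 0.3 and c = 0.5 the ratio is 1 + 0.5 × 0.7/0.3 = 2.17.

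**In participants.** Take p = 0.2, q = 0.6 and c = 0.3:
- Control: 0.2 × 0.6 = 0.120, and 77 × 0.120 = 9.2 expected.
- Interview arm: 0.2 × (0.6 + 0.4 × 0.3) = 0.144, and 77 × 0.144 = 11.1 expected.

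In 200,000 simulated pairs of binomial counts with these values, the interview arm had the higher count in about 62% and the lower in about 29%. With c = 0 the two figures were both about 45%, the rest being ties.

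**If control contacts also reveal events.** Let them pick up a share d of those the questionnaire misses. The ratio becomes [q + (1 − q)c]/[q + (1 − q)d], which is 1 when d = c. The undefined control sessions therefore matter: the table above assumes d = 0.

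**The case against.** The strongest reply is that nothing in the documents makes the calls a source of adverse events. Section 11 describes them as motivational interviews about activity, and the only collection method that Section 22 names goes to both arms. On that reading c is 0 and the recorded ratio is 1.00. Control sessions, reminder calls and drop-out reasons could also bring events to light in controls.

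Much of this stands. A reader might infer that Section 22 orders recording from any source and that recorded harms will be higher in the interview arm. The first is not in the text, and the second depends on c and d, which the documents leave open. A reader might also infer that a between-arm harms comparison is part of the plan. None is specified, and safety is not among the hypotheses in Section 7.

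The reply does not remove the point. If events heard in calls are recorded, detection may differ by arm. If they are not, the promise to record all events is not kept. Section 22 needs a rule in either case. Reminder calls follow only lapsed synchronization, so they are not equivalent to seven scheduled calls.

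It might also seem natural to leave events known only from calls out of all arm counts. That goes too far: the questionnaire item covers only monitor- or activity-related events and misses participants who do not answer it, so real events would drop out of the comparison by arm.

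**Conclusion.** The point holds as a conditional one. As written, Section 22 lets adverse events enter the record through contacts that Section 11 schedules in one arm only, so recorded harms could be higher in the interview arm at equal true rates. The possible size runs from nil (ratio 1.00 if calls feed no log) to about 1.01 to 2.17 for c of 0.1 to 0.5 and q of 0.9 to 0.3. These values are assumed. The calculation also assumes equal questionnaire capture in both arms and no pick-up through control contacts. The documents do not show that an excess will occur. The gap should be closed because it affects how any by-arm harms table can be read, and closing it is cheap.

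**What to change.** In Section 22:

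1. Add a source field to every adverse event entry: questionnaire, interview call or other contact. This also makes explicit that events mentioned in calls are recorded.
2. Make questionnaire-reported events the primary between-arm harms summary. Label it as monitor- or activity-related and show the number of respondents per arm.
3. Tabulate all recorded events by arm and source, with a statement that contact differed by arm. No event, including those in drop-outs and non-responders, is then left out of the report.
4. Keep the source field from the blinded analyst until the main analysis is done, because an interview-call entry reveals allocation and Section 17 has the principal investigator analyze the data blinded.
5. Reconcile the mention of control sessions in Sections 11.b and 19 with the control description in Section 11.

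The cost is a few sentences, one field in the adverse event log and one extra table. The primary harms summary will use fewer events and cover a narrower type than Section 22 defines. Differences between arms in recall or questionnaire response may remain, since repeated calls could affect both. Showing respondents per arm makes differential response visible, but not differential recall.

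### Section 22 promises to record every adverse event whatever its cause, but the only question described asks about events tied to the monitor or to being more active

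*Combined protocol and SAP*

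**What the plan says.** Section 22 (Harms) makes four statements whose scope does not depend on cause:

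- An adverse event is defined "without regard to the possibility of a causal relationship with the intervention".
- On timing: "Adverse events will be collected after the subject has provided consent and enrolled in the study".
- If an event occurs after consent but before the intervention has started, "the event will be reported as not related to the intervention".
- On completeness: "All adverse events occurring after entry into the study will be recorded".

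The section closes with the one active enquiry it describes: "The participants will be asked at the end-point questionnaire if they experienced any adverse events in terms of using the PAMs". Read to its end, the sentence limits the question to "any adverse events in terms of using the PAMs or trying to enhance their daily amount of physical activity".

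Section 18a gives the timing: "On the last day of intervention (day 84), the participants will receive a similar SurveyXact invitation with the end-point questionnaire". Section 18b adds a possible indirect source: "If possible, reasons for drop out will be collected from each discontinued participant".

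**The concern.** The definition and the promise take in every untoward event after consent. The question described takes in only those that the participant connects with the monitor or with trying to be more active. The judgement of cause that the definition sets aside is thus brought back at the point of collection, and the participant makes it.

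Participants are at least 70 years old and both arms are encouraged to increase their activity. Whether a fall, an injury or a hospital contact had anything to do with that activity is often unclear to the person concerned. If such events are not asked about, a published count of adverse events would be read under the all-cause definition although a narrower question produced it.

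**Working it through.** No arithmetic bears on this point. It is a check of the text against itself, in two steps.

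**Step 1. What is promised against what is asked.** The promised set is all untoward medical events from consent onward. The asked set is those linked to the monitor or to trying to be more active, as reported on a questionnaire sent on day 84 (12 × 7 = 84).

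| Type of event | Within the promise? | Within the question as described? |
|---|---|---|
| During the 12 weeks, linked by the participant to monitor or activity | Yes | Yes |
| During the 12 weeks, not so linked | Yes | No |
| After consent but before the intervention, linked to monitor or activity | Yes, reported as unrelated | Possibly: Section 22 gives the question no start date |
| After consent but before the intervention, not so linked | Yes, reported as unrelated | No |

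The last two rows are not hypothetical. Under Section 16.a randomization follows the baseline step count, is done weekly, and is skipped in weeks with fewer than four new participants. Time can therefore pass between consent and the start of the intervention.

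**Step 2. Whether another section supplies the missing enquiry.**

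- Section 9: contact is by phone or e-mail only, so there is no visit at which events could be noted.
- Section 11: the experimental arm has calls in weeks 1, 2, 3, 5, 7, 9 and 12, seven in all. Their described content does not include adverse events. The control intervention lists no calls, although Sections 11.b and 19 mention control sessions in connection with audiotaping.
- Section 12: the 6- and 12-month surveys are described as repeating the secondary outcomes, and adverse events are not among these.
- Section 18b: a call is made when a lapse in synchronization suggests drop-out, and drop-out reasons are sought where possible. Neither is described as adverse event collection.
- Sections 21 and 23: data monitoring is marked as not applicable and no auditing is planned.

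None of these describes an all-cause enquiry. The questionnaire itself is not in the documents. The timeline figure in Section 13 and some front and end matter could not be checked.

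**The case against.** The strongest reply is that Section 22 makes separate commitments. It says that events will be collected and recorded, then adds a targeted question, and nowhere says that the question is the only route. General recording plus one targeted question would be coherent, and routes for spontaneous reports exist by phone and e-mail. This stands in part. A reader might infer that all other events will go unrecorded, and the documents do not support that. But no route, form, responsible person or frequency is given for general recording. If it relied on what comes up in conversation, the seven scheduled calls would give the experimental arm more opportunity to report than the control arm.

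The wording quoted is also loose, and the actual questionnaire may be broader. This limits the point to what Section 22 describes. If the questionnaire is broader, Section 22 misdescribes it and still needs correcting.

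A reader might further infer that nothing before the intervention could be captured. That goes too far, since events in that period linked to the monitor or to activity may fall within the question.

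Finally, the intervention is low risk. Section 24 records that the trial was not subject to research-ethics law because the intervention is non-invasive and behavioural. This bears on how much the point matters, but it does not remove the inconsistency.

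**Conclusion.** The point holds as an inconsistency within Section 22. The question as described filters by perceived cause, so it cannot by itself deliver the promised all-cause record, and no other enquiry is described. A harms count based on it would be narrower than the protocol's own definition.

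The limited scope applies to all 154 planned participants. The number of events missed cannot be estimated, because the documents give no adverse event rate. The attrition allowance in Section 14 does not help: it is not a questionnaire return rate, and non-return is a different problem from the scope of the question.

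The step-count analysis, the sample size and the efficacy conclusion are unaffected. A reader might infer a biased comparison of harms between arms. The documents do not support that: Section 20 plans no such comparison, and Section 18a sends the end-point questionnaire to participants without distinction by arm.

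The conclusion rests on two assumptions: that Section 22 describes the question accurately, and that the material that could not be checked contains no broader enquiry.

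**What to change.** Reword the end-point question, for both arms, to ask about any untoward medical event since consent, whatever its perceived cause, with falls, injuries and hospital contact as prompts. Ask the same when drop-out reasons are collected. If other events are meant to be recorded by another route, describe that route in Section 22 and make it the same in both arms.

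The alternative is to narrow the definition and the promise in Section 22 to the events actually asked about, and to report the count on that basis.

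The first option changes one item in an existing online questionnaire and adds an enquiry at drop-out. Its cost is more events to code, probably mostly unrelated and of unknown number. It would still miss participants who continue but do not return the questionnaire after the reminders. The second option is only a text edit, but it gives up all-cause safety data.
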